5.7.4. Definition of Subgroups

Selected safety and immunogenicity analyses will be conducted by the age group of the participant.

Immunogenicity subanalyses will be performed by BMI, sex and race.

5.8. Interim Analyses

This SAP applies to all planned analyses of this study per CTP section 9.5 (Interim Analyses; Primary Analysis and Final Analysis). After the first database lock, separate SAP document(s) may be written as needed to cover specific analysis needs that cannot be documented elsewhere (e.g. in the Data Presentation Specifications [DPS] document).

5.8.1. Data Monitoring Committee (DMC) or Other Review Board

An internal DRC was commissioned for this study. However, an independent IDMC was installed to include VAC31518COV2001 on 29 October 2020. Please refer to the IDMC Charter.

6. SUPPORTING DOCUMENTATION

6.1. Appendix 1 List of abbreviations

AE	adverse event
AESI	Adverse event of special interest
BMI	Body Mass Index
CI	confidence interval
CoV	Corona Virus
COVID-19	Corona Virus Disease 2019
CRF	case report form
CSR	Clinical Study Report
CTP	Clinical Study Protocol
DMC	Data Monitoring Committee
DPS	Data Presentation specifications
DRC	Data Review Committee
eCRF	electronic case report form
ELISA	Enzyme-linked immunosorbent assay
ELISpot	enzyme-linked immunospot
FAS	Full Analysis Set
FDA	Food and Drug Administration
FOIA	Freedom of Information Act
FU	Follow-up
GMC	Geometric mean concentration
GMT	Geometric mean titer
ICH	International Conference on Harmonization
ICS	Intracellular Cytokine Staining
IFN- γ / IFN-g	Interferon gamma
IL	Interleukin
ITT	Intent-to-Treat
IU/ml	International units per milliliter
IWRS	interactive web response system
kg	Kilogram
LLOQ	lower limit of quantification
LOD	Limit of detection
m	meter
Max	Maximum
MedDRA	Medical Dictionary for Regulatory Activities
Min	Minimum
N	Number
NA	Not Applicable
PBMC	peripheral blood mononuclear cell
PD	Pharmacodynamic
PF4	Antibodies to platelet factor 4
PI	principal investigator
PK	pharmacokinetic(s)
PP	Per Protocol
PPI	Per Protocol Immunogenicity Set
PRO	Patient Reported Outcome
Q1	First quartile
Q3	Third quartile
RNA	Ribonucleic acid
S	Spike
SAE	serious adverse event
SAP	Statistical Analysis Plan
SARS	Severe acute respiratory syndrome
SARS-CoV-2	Severe acute respiratory syndrome coronavirus-2

SD	standard deviation
SDTM	Study Data Tabulation Model
SE	Standard error
SIC	Symptoms of Infection with COVID-19
Th1	Helper cell type 1
Th2	Helper cell type 2
TLF	Tables, Listings and Figures
TNF- α / TNF-a	Tumor necrosis factor alpha
ULOQ	Upper limit of quantification
VNA	Virus Neutralization Assay
WHO	World Health Organization

6.2. Appendix 2 Changes to Protocol-Planned Analyses

In October 2020, the current study was temporarily paused because one of the pausing rules was met in study COV3001. When the pause was lifted, most of the participants in Groups 7-8 had missed their visit window for Vaccination 2, rendering the intent of the 28-day vaccination interval in these groups futile.

For safety analyses,

- the 2 subjects vaccinated before pausing rule (28-day interval) will only be shown in the listings.
- the other subjects received the vaccination 2 between 51 and 72 days after Vaccination 1. They will be integrated in the Full Analysis Set with groups 1 and 6 (56-day interval).

For immunogenicity analyses,

- subjects randomized in groups 7 and 8 won't be included in PPI set
- a modified PPI set will be defined as follows :
subjects with vaccination 2 within the window (54-64) or subjects who did not receive vaccination 2 will be integrated in groups 1 and 6
- a modified FAS set will be defined as follows :
subjects in mPPI set and subjects with vaccination 2 in (51-53) days or (65-72) days window

6.3. Appendix 3 Guidance for Industry: Toxicity Grading Scale for Healthy Adult and Adolescent Volunteers Enrolled in Preventive Vaccine Clinical Trials

The laboratory values provided in the tables below serve as guidelines and are dependent upon institutional normal parameters. Institutional normal reference ranges should be provided to demonstrate that they are appropriate.

If a laboratory value falls within the grading as specified below but also within the local laboratory normal limits, the value is considered as normal.

Serum *	Mild (Grade 1)	Moderate (Grade 2)	Severe (Grade 3)	Potentially Life Threatening (Grade 4)**
Sodium – Hyponatremia mEq/L	132 – 134	130 – 131	125 – 129	< 125
Sodium – Hypernatremia mEq/L	144 – 145	146 – 147	148 – 150	> 150
Potassium – Hyperkalemia mEq/L	5.1 – 5.2	5.3 – 5.4	5.5 – 5.6	> 5.6
Potassium – Hypokalemia mEq/L	3.5 – 3.6	3.3 – 3.4	3.1 – 3.2	< 3.1
Glucose – Hypoglycemia mg/dL	65 – 69	55 – 64	45 – 54	< 45
Glucose – Hyperglycemia Fasting – mg/dL Random – mg/dL	100 – 110 110 – 125	111 – 125 126 – 200	>125 >200	Insulin requirements or hyperosmolar coma
Blood Urea Nitrogen BUN mg/dL	23-26	27 – 31	> 31	Requires dialysis
Creatinine – mg/dL	1.5 – 1.7	1.8 – 2.0	2.1 – 2.5	> 2.5 or requires dialysis
Calcium – hypocalcemia mg/dL	8.0 – 8.4	7.5 – 7.9	7.0 – 7.4	< 7.0
Calcium – hypercalcemia mg/dL	10.5 – 11.0	11.1 – 11.5	11.6 – 12.0	> 12.0
Magnesium – hypomagnesemia mg/dL	1.3 – 1.5	1.1 – 1.2	0.9 – 1.0	< 0.9
Phosphorous – hypophosphatemia mg/dL	2.3 – 2.5	2.0 – 2.2	1.6 – 1.9	< 1.6
CPK – mg/dL	1.25 – 1.5 x ULN***	1.6 – 3.0 x ULN	3.1 – 10 x ULN	> 10 x ULN
Albumin – Hypoalbuminemia g/dL	2.8 – 3.1	2.5 – 2.7	< 2.5	--
Total Protein – Hypoproteinemia g/dL	5.5 – 6.0	5.0 – 5.4	< 5.0	--
Alkaline phosphate – increase by factor	1.1 – 2.0 x ULN	2.1 – 3.0 x ULN	3.1 – 10 x ULN	> 10 x ULN
Liver Function Tests –ALT, AST increase by factor	1.1 – 2.5 x ULN	2.6 – 5.0 x ULN	5.1 – 10 x ULN	> 10 x ULN
Bilirubin – when accompanied by any increase in Liver Function Test increase by factor	1.1 – 1.25 x ULN	1.26 – 1.5 x ULN	1.51 – 1.75 x ULN	> 1.75 x ULN
Bilirubin – when Liver Function Test is normal; increase by factor	1.1 – 1.5 x ULN	1.6 – 2.0 x ULN	2.0 – 3.0 x ULN	> 3.0 x ULN
Cholesterol	201 – 210	211 – 225	> 226	---
Pancreatic enzymes – amylase, lipase	1.1 – 1.5 x ULN	1.6 – 2.0 x ULN	2.1 – 5.0 x ULN	> 5.0 x ULN

* The laboratory values provided in the tables serve as guidelines and are dependent upon institutional normal parameters. Institutional normal reference ranges should be provided to demonstrate that they are appropriate.

** The clinical signs or symptoms associated with laboratory abnormalities might result in characterization of the laboratory abnormalities as Potentially Life Threatening (Grade 4). For example, a low sodium value that falls within a grade 3 parameter (125-129 mE/L) should be recorded as a grade 4 hyponatremia event if the participant had a new seizure associated with the low sodium value.

***"ULN" is the upper limit of the normal range.

Hematology *	Mild (Grade 1)	Moderate (Grade 2)	Severe (Grade 3)	Potentially Life Threatening (Grade 4)
Hemoglobin (Female) - gm/dL	11.0 – 12.0	9.5 – 10.9	8.0 – 9.4	< 8.0
Hemoglobin (Female) change from baseline value - gm/dL	Any decrease – 1.5	1.6 – 2.0	2.1 – 5.0	> 5.0
Hemoglobin (Male) - gm/dL	12.5 – 13.5	10.5 – 12.4	8.5 – 10.4	< 8.5
Hemoglobin (Male) change from baseline value – gm/dL	Any decrease – 1.5	1.6 – 2.0	2.1 – 5.0	> 5.0
WBC Increase - cell/mm ³	10,800 – 15,000	15,001 – 20,000	20,001 – 25,000	> 25,000
WBC Decrease - cell/mm ³	2,500 – 3,500	1,500 – 2,499	1,000 – 1,499	< 1,000
Lymphocytes Decrease - cell/mm ³	750 – 1,000	500 – 749	250 – 499	< 250
Neutrophils Decrease - cell/mm ³	1,500 – 2,000	1,000 – 1,499	500 – 999	< 500
Eosinophils - cell/mm ³	650 – 1500	1501 - 5000	> 5000	Hypereosinophilic
Platelets Decreased - cell/mm ³	125,000 – 140,000	100,000 – 124,000	25,000 – 99,000	< 25,000
PT – increase by factor (prothrombin time)	1.0 – 1.10 x ULN**	1.11 – 1.20 x ULN	1.21 – 1.25 x ULN	> 1.25 ULN
PTT – increase by factor (partial thromboplastin time)	1.0 – 1.2 x ULN	1.21 – 1.4 x ULN	1.41 – 1.5 x ULN	> 1.5 x ULN
Fibrinogen increase - mg/dL	400 – 500	501 – 600	> 600	--
Fibrinogen decrease - mg/dL	150 – 200	125 – 149	100 – 124	< 100 or associated with gross bleeding or disseminated intravascular coagulation (DIC)
International Normalized Ratio (INR)***	1.1 to < 1.5 x ULN	1.5 to < 2.0 x ULN	2.0 to < 3.0 x ULN	≥ 3.0 x ULN

* The laboratory values provided in the tables serve as guidelines and are dependent upon institutional normal parameters. Institutional normal reference ranges should be provided to demonstrate that they are appropriate.

** "ULN" is the upper limit of the normal range.

***: For INR, the values in the table are based on the Division of AIDS Table for Grading the Severity of Adult and Pediatric Adverse Events, 2014 (version 2.0)

Urine *	Mild (Grade 1)	Moderate (Grade 2)	Severe (Grade 3)	Potentially Life Threatening (Grade 4)
Protein	Trace	1+	2+	Hospitalization or dialysis
Glucose	Trace	1+	2+	Hospitalization for hyperglycemia
Blood (microscopic) - red blood cells per high power field (rbc/hpf)	1 - 10	11 - 50	> 50 and/or gross blood	Hospitalization or packed red blood cells (PRBC) transfusion

* The laboratory values provided in the tables serve as guidelines and are dependent upon institutional normal parameters. Institutional normal reference ranges should be provided to demonstrate that they are appropriate.

Vital Signs *	Mild (Grade 1)	Moderate (Grade 2)	Severe (Grade 3)	Potentially Life Threatening (Grade 4)
Fever (°C) ** (°F) *	38.0 – 38.4 100.4 – 101.1	38.5 – 38.9 101.2 – 102.0	39.0 – 40 102.1 – 104	> 40 > 104
Tachycardia - beats per minute	101 – 115	116 – 130	> 130	ER visit or hospitalization for arrhythmia
Bradycardia - beats per minute***	50 – 54	45 – 49	< 45	ER visit or hospitalization for arrhythmia
Hypertension (systolic) - mm Hg	141 – 150	151 – 155	> 155	ER visit or hospitalization for malignant hypertension
Hypertension (diastolic) - mm Hg	91 – 95	96 – 100	> 100	ER visit or hospitalization for malignant hypertension
Hypotension (systolic) – mm Hg	85 – 89	80 – 84	< 80	ER visit or hospitalization for hypotensive shock
Respiratory Rate – breaths per minute	17 – 20	21 – 25	> 25	Intubation

* Participant should be at rest for all vital sign measurements.

** Oral temperature; no recent hot or cold beverages or smoking.

*** When resting heart rate is between 60 - 100 beats per minute. Use clinical judgement when characterizing bradycardia among some healthy participant populations, for example, conditioned athletes.

Ranges to convert FDA scale to SI units

Ranges to convert FDA scale to SI units		Mild (Grade 1)	Moderate (Grade 2)	Severe (Grade 3)	Potentially Life threatening (Grade 4)
Albumin (g/L)	Hypo-albuminemia	28-31	25-27	<25	
Eosinophils (10 ⁹ /L)		0.65-1.5	1.501-5.0	>5.0	
Hemoglobin for male (g/L)		125-135	105-124	85-104	<85
Hemoglobin for female (g/L)		110-120	95-109	80-94	<80
Hemoglobin change from baseline (g/L)		Any decrease - 15	16-20	21-50	>50
Lymphocytes (10 ⁹ /L)		0.75-1.0	0.5-0.749	0.25-0.499	<0.25
Neutrophils (10 ⁹ /L)		1.5-2.0	1.0-1.499	0.5-0.999	<0.5
Platelets (10 ⁹ /L)		125-140	100-124	25-99	<25
Protein (g/L)	Hypo-proteinemia	55-60	50-54	<50	
WBC (10 ⁹ /L)	Increase	10.8-15	15.001-20	20.001-25	>25
	Decrease	2.5-3.5	1.5-2.499	1.0-1.499	<1.0

Other Conversions

Blood, Serum, or Plasma Chemistries ^[1]		Mild (Grade 1)	Moderate (Grade 2)	Severe (Grade 3)	Potentially Life-threatening (Grade 4)	Conversion factor
Glucose (mmol/L)	Hypoglycemia	3.61-3.83	3.05-3.60	2.50-3.04	<2.50	18.01477
	Hyperglycemia-Fasting	5.55-6.11	6.12-6.94	>6.94		
	Hyperglycemia-Random	6.11-6.94	6.95-11.10	>11.10		
Blood urea nitrogen (mmol/L)		8.2-9.3	9.4-11.1	>11.1		
Creatinine (μmol/L)		133-150	151-177	178-221	>221	0.01131
Calcium (mmol/L)	Hypocalcemia	2.00-2.10	1.87-1.99	1.75-1.86	<1.75	4
	Hypercalcemia	2.62-2.74	2.75-2.87	2.88-3.00	>3.00	4
Magnesium (mmol/L)	Hypomagnesemia	0.53-0.62	0.45-0.52	0.37-0.44	<0.37	2.43072
Phosphorus (mmol/L)	Hypophosphatemia	0.74-0.81	0.65-0.73	0.52-0.66	<0.52	3.09693

^[1] Depending upon the laboratory used, reference ranges, eligibility ranges and grading may be split out by sex and/or age.

Cholesterol (mmol/L)		5.20-5.43	5.44-5.82	>5.82		
Coagulation						
Fibrinogen (μ mol/L)	Increase	11.76-14.70	14.71-17.65	>17.65		
	Decrease	4.41-5.88	3.68-4.40	2.94-3.67	<2.94	/34

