9.4.2. Primary/Secondary Endpoints

Immunogenicity Endpoints

Descriptive statistics (geometric mean and confidence intervals, or median and interquartile range Q1-Q3, as appropriate) will be calculated for continuous immunologic parameters. Several definitions of serological response will be applied (fold increases in GMT [VNA] or GMC [ELISA]). Graphical representations of immunologic parameters will be made as applicable. Frequency tabulations will be calculated for discrete (qualitative) immunologic parameters, as applicable.

In addition, the ratio between neutralizing and binding antibodies as determined by VNA and S protein ELISA, respectively, will be calculated together with confidence intervals.

For adults, all data will be analyzed separately from the point of unblinding for safety and immunogenicity. Details will be described in the SAP.

For adolescents, limited pooled safety and reactogenicity data (planned for IDMC review) and group unblinded immunogenicity data (summary of S-ELISA, including GMC, and seroresponse rates for all participants and seronegative at baseline participants, in Ad26.COV2.S 2.5x10¹⁰ vp only) were reviewed by the sponsor prior to Amendment 6 (see Section 4.1 Overall Design).

The immunogenicity analyses will be performed on the PPI population. Immunogenicity analyses will also be done on the FAS (participants who became infected during the study will be analyzed as a subgroup and shown in the graphs using different colors and symbols).

Safety Endpoints

No formal statistical testing of safety data is planned. Safety data will be analyzed descriptively by vaccine group. In addition, for selected tables, tabulations pooled by vaccine dose will also be provided. All safety analyses will be done on the FAS.

Adverse Events

The verbatim terms used in the eCRF by investigators to identify AEs will be coded using the Medical Dictionary for Regulatory Activities (MedDRA). All reported AEs will be included in the analysis. (S)AEs caused by molecularly confirmed SARS-CoV-2 infection will be removed at the analysis level from the (S)AE listings and tables and presented separately. For each AE, the percentage of participants who experience at least one occurrence of the given event will be summarized by vaccine group.

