4. POPULATIONS (ANALYSIS SETS) FOR ANALYSIS

For vaccine studies, study intervention assignment will follow the as treated principle: all analyses (including safety, immunogenicity and efficacy analyses) will be analyzed by the actually received vaccine.

Population	Description
All screened participants (ALL)	The “all screened participants” set includes all participants that were screened, regardless of whether they were enrolled and/or randomized.
All randomized participants (ALL RANDOMIZED)	The “all randomized participants” set includes all participants that were randomized to one of the treatment groups.
Full Analyses Set (FAS)	The full analysis set will include all participants with at least one vaccine administration documented.
Per Protocol Immunogenicity Set (PPI)	The per protocol immunogenicity population will include all randomized and vaccinated participants for whom immunogenicity data are available. Samples taken after a participant meets the criteria for a major protocol deviation expected to impact the immunogenicity outcomes will be excluded from the PPI analysis. In addition, samples obtained after missed vaccinations or participants with natural infection occurring after screening (if applicable) will be excluded from the analysis set. SARS-CoV-2 infection is defined as a positive PCR test or positive N-serology.

Two additional analysis sets are defined in Appendix 2 : PPI modified and FAS modified.

The safety and COVID-19 cases analyses will be censored at the date of unblinding or the receipt of an unscheduled vaccine^a, whichever event occurs first. AEs and COVID episodes reported after unblinding or receipt of an unscheduled vaccine, whichever comes first, will be listed.

The immunogenicity analyses will be censored at the date of the receipt of

- an unscheduled vaccine,
- another live vaccine,
- unknown vaccine which is received in the window of +/-29 days at each dosing,
- other not live vaccine which is received in the window of +/-15 days at each dosing.

Immunogenicity samples excluded for the above reasons will be included in the listings and flagged.

^a Unscheduled vaccine: an authorized/licensed COVID-19 vaccine offered outside of the study.

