Safety analyses will be performed on the FAS. Continuous variables will be summarized using the following statistics, as appropriate: number of observations, arithmetic mean (mean), standard deviation (SD), standard error (SE), median, quartiles (Q1 and Q3), minimum and maximum. Frequencies and percentages (one decimal place) will be generated for categorical variables. No formal comparisons between groups will be provided.

Safety data will be analyzed by study intervention regimens as designed per protocol^a. In addition, safety data will be analyzed by intervention regimens as designed per protocol and age group. Data will be presented by period (post Dose 1, post Dose 2, post Antigen Presentation, as applicable) as well as over the entire primary regimen, and over the entire Antigen Presentation regimen. Denominator for the percentages is the number of participants in the considered population and phase for a certain regimen (incidence per 100 participants/phase).

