5.6.1.2. Analysis of Adverse Events

Number and percentage of participants with at least one particular AE (unsolicited/solicited) will be tabulated. Unsolicited AEs will be summarized by System Organ Class and Preferred Term. Solicited AEs will be summarized by class (administration site/systemic) and Preferred Term.

For solicited AEs following tables will be provided: summary, by worst severity grade, at least grade 3, related (systemic only), time to onset (in days) and duration (in days) for most frequent events and body temperature. Note: Duration is defined as number of days from the start of the event until resolution of the event. The time to first onset is defined as (date of first onset – reference date + 1). The reference date is the start date of the vaccination period.

For unsolicited AEs, the following tables will be provided: summary table (including SAE, fatal outcome, and discontinuation), all events, most frequent, at least grade 3, permanent stop of vaccine, related, and SAE.

As a general remark, COVID-19 cases will be analyzed separately (see section 5.7.3).

- SAEs that are COVID-19 related will not be included in the SAE tables, but will be included and flagged in the SAE listings. In MedDRA version 23.0, Preferred Terms (PT codes) “COVID-19 (10084268)”, “COVID-19 pneumonia (10084380)”, “Suspected COVID-19” (10084451), and “Asymptomatic COVID-19 (10084459)”, “Coronavirus infection” (10051905), “Severe acute respiratory syndrome” (10061982), “SARS-CoV-2 carrier” (10084461), “Exposure to SARS-CoV-2” (10084456) and “Occupational exposure to SARS-CoV-2” (10084394) will be considered COVID-19 related AEs^a.

Listings and/or participant narratives will be provided as appropriate, for those participants who die, discontinue study vaccinations due to an AE, or experience a severe or serious AE.

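### SAP Appendix 2 takes two FAS participants out of every safety table and does not say where Group 7–8 participants without Vaccination 2 are counted for safety

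*SAP*

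**What the plan says.** The pause meant that nearly all of Groups 7 and 8 missed the 28-day window for Vaccination 2. SAP 6.2 (Appendix 2) handles this with separate safety and immunogenicity rules.

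- **Safety, the two dosed on schedule:** "the 2 subjects vaccinated before pausing rule (28-day interval) will only be shown in the listings".
- **Safety, everyone else:** "the other subjects received the vaccination 2 between 51 and 72 days after Vaccination 1. They will be integrated in the Full Analysis Set", together with Groups 1 and 6.
- **Immunogenicity, modified PPI:** "subjects with vaccination 2 within the window (54-64) or subjects who did not receive vaccination 2 will be integrated in groups 1 and 6".
- **Immunogenicity, modified FAS:** "subjects in mPPI set and subjects with vaccination 2 in (51-53) days or (65-72) days window".

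The governing set for safety is stated in both documents. Protocol 9.4.2 has "All safety analyses will be done on the FAS" and SAP 5.6 has "Safety analyses will be performed on the FAS". SAP 4 defines the set: "The full analysis set will include all participants with at least one vaccine administration documented". It does not require a second dose.

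The tables concerned are in SAP 5.6.1.2. For unsolicited events they include a summary with SAEs, deaths and discontinuations, and then tables for "most frequent, at least grade 3, permanent stop of vaccine, related, and SAE".

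**The concern.** There are two separate problems.

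The first is an explicit exclusion. Two vaccinated participants who meet the FAS definition are removed from all safety tables because of when they received dose 2. That reason cannot apply to what happened before dose 2.

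The second is an omission. The safety rule describes the remaining participants by a post-baseline fact, receipt of Vaccination 2 at 51–72 days, and says nothing about anyone who did not receive it. The immunogenicity rule a few lines later does name and place such participants. Groups 1 and 6 keep their own dose-1-only participants. If a programmer used the 51–72 day wording as an entry condition, the merged columns would combine one group followed from dose 1 with another selected for having reached dose 2. Tables of vaccine stopping and of early SAEs are the ones most exposed to such selection. SAEs from first vaccination onward are a primary endpoint for adults.

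**Working it through.** The plan states no figure on this point, so the check is of which participants each rule covers, followed by arithmetic on planned sizes.

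**Inputs.** Planned sizes are Group 1 = 75, Group 6 = 25, Group 7 = 50 and Group 8 = 25 (Protocol 4.1, Table 2). One participant in each of Groups 7 and 8 was dosed at 28 days (Protocol 4.1, footnote on Groups 7 and 8). The day windows come from SAP 6.2. The number of Group 7–8 participants without Vaccination 2 is not given anywhere.

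**Step 1: exposure of the two.** In Protocol Table 2, Groups 7 and 1 receive the same Day 1 dose, and Groups 8 and 6 both receive placebo. SAP 5.1.2 (Table 1) closes the post-dose-1 period at 28 days or just before dose 2, whichever is earlier. The Group 7–8 window for Vaccination 2 is Day 29 ± 3, so an in-window dose shortens that period by 3 days at most. Within it their exposure is that of Groups 1 and 6.

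**Step 2: coverage of the rules.**

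| Group 7–8 participants | Safety rule | Immunogenicity rule |
|---|---|---|
| Vaccination 2 at 28 days (2 people) | listings only | in neither modified set |
| Vaccination 2 at 54–64 days | with Groups 1 and 6 | modified PPI |
| Vaccination 2 at 51–53 or 65–72 days | with Groups 1 and 6 | modified FAS |
| No Vaccination 2 | not mentioned | modified PPI, with Groups 1 and 6 |

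The three windows cover 3 + 11 + 8 = 22 days, which is exactly 51 to 72. As classes, the modified FAS is therefore the safety group as literally described plus those without Vaccination 2. That last class is the only difference.

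**Step 3: size of the explicit exclusion.** Merged columns holding everyone would be 75 + 50 = 125 active and 25 + 25 = 50 placebo. Removing one from each leaves 124 and 49. The zero-event one-sided 95% upper limit is 1 − 0.05^(1/n). This formula reproduces Protocol Table 9: 11.29%, 5.82%, 3.92% and 1.98% against the stated 11.3%, 5.8%, 3.9% and 2.0%. The limit moves from 2.37% to 2.39% (active) and from 5.82% to 5.93% (placebo).

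**Step 4: conditional illustration of the omission.** Assume 51–72 days is used as a filter. Assume also that a true share r stops vaccine for an AE after dose 1 in every group, that every missed dose 2 is such a stop, and that no later stops are counted. The merged columns then show 75r/(124 − 49r) for active and 25r/(49 − 24r) for placebo.

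| r | Active column | Placebo column |
|---|---|---|
| 2% | 1.50/123.02 = 1.2% | 0.50/48.52 = 1.0% |
| 5% | 3.75/121.55 = 3.1% | 1.25/47.80 = 2.6% |
| 10% | 7.50/119.10 = 6.3% | 2.50/46.60 = 5.4% |

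If Group 10 shared the placebo column, the dilution there would be to about 50/74 = 0.68 of the true rate instead of about half. If nobody missed Vaccination 2, the effect is zero. Denominators alone matter little: with 10 active participants left out (114 instead of 124), the zero-event limit moves from 2.39% to 2.59%.

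**The case against.** A reader might infer that Appendix 2 admits Group 7–8 participants to safety tables only if they received Vaccination 2 late, so that those who stopped after dose 1 vanish from the dose-1, stopping and SAE tables. The documents do not support that. The rule has no such condition. Its two classes, the two on-schedule participants and the others, can plainly be read as covering all of Groups 7–8, with the 51–72 day clause as a description. One dose is enough for the FAS, and Appendix 2 does not change that definition. SAP 5.1.5 also keeps groups separate unless pooling is stated, so an unplaced participant could stay in Group 7 or 8. No document says that anyone in these groups missed Vaccination 2.

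Other safeguards exist. SAP 5.2 counts discontinuations by regimen. SAP 5.6.1.2 provides listings or narratives, as appropriate, for deaths, vaccine discontinuations due to AEs, and severe or serious events. SAP 5.6 plans no formal group comparisons. Column details may be in the Data Presentation Specifications, which are not available here. The handling of the two on-schedule participants is disclosed and concerns one person per column.

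Most of this stands, and it rules out calling the omission an exclusion. Three things remain. Disclosure does not reconcile the listings-only rule with the requirement that all safety analyses use the FAS. FAS membership does not assign a table column. And leaving unplaced participants in their own group would still leave the merged columns selected on receipt of dose 2.

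**Conclusion.** The point holds in two parts of different strength.

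The exclusion of the two participants dosed at 28 days is certain from the text. It conflicts with the FAS rule and has no rationale for post-dose-1 data. Its numerical effect is small: one participant per merged column.

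The handling of participants without Vaccination 2 is unspecified for safety, although the same appendix specifies it for immunogenicity. That is an ambiguity, not a stated exclusion. It would bias results only if such participants exist and the 51–72 day wording is applied as a filter. Neither is shown. The Step 4 percentages are conditional illustrations and should not be cited as an estimate of bias in this trial. Participants who had a reaction or an SAE and still received dose 2 are counted on any reading.

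The change is worth making because primary safety tables are involved and the correction is simple.

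**What to change.** Replace the two safety bullets in SAP 6.2 with text to this effect:

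- All Group 7–8 participants in the FAS, including any without Vaccination 2 and the two dosed at 28 days, are counted with Groups 1 and 6 in the post-dose-1 tables.
- Participants without Vaccination 2 stay in those columns for the permanent-stop and Entire Period SAE/AESI tables, matching the modified PPI rule.
- Post-dose-2 tables include those who received Vaccination 2 at 51–72 days. Data after Vaccination 2 for the two participants dosed at 28 days are listed, with a footnote to the tables.

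It would also help to state how many Group 7 and Group 8 participants did not receive Vaccination 2, since that number settles whether the second part has any effect.

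The cost is a few sentences of SAP text, a change to column assignment in the programs, and a footnote. No data collection or clinical procedure changes.
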